## 9.8. Concomitant Medications

Refer to [Section 9.1.2](#).

## 9.9. Other Safety Measures

### 9.9.1. 12-Lead Standard Electrocardiogram

Unscheduled ECG measurements will be included in listings but will be excluded from tabular and graphical summaries by time point, except when calculating the maximum severity post baseline. Baseline is defined in [Section 3.1](#). Individual interval measurements and overall interpretations will be presented in [Listing 19](#) and [Listing 20](#), respectively.

---

The sort order for ECG interval measurements will be as follows: PR Interval, QRS Interval, QT Interval, QTcF Interval, RR Interval, and Ventricular Rate.

12-lead standard ECG results will be summarized in tables and figures:

- Summary of 12-lead standard ECG change in overall interpretation from baseline will be shown by treatment group and time point (**Table 38**).
- Number and percentage of participants with mild, moderate, severe, or life-threatening ECG results by parameter, time point, and treatment group (**Table 39**).

#### 9.9.2. Tolerability

Tolerability to study product is summarized by treatment group in **Table 14**. The table includes number and percentage of participants who (1) were terminated early or withdrawn due to TEAE related to study product; (2) had at least one TEAE; (3) had at least one Grade 3 abnormal lab test, VS measurement, or ECG parameter; (4) completed all oral medication doses.

## 10. PHARMACOKINETICS

The PK Analysis Population will be used when summarizing plasma drug concentrations and will be used to conduct noncompartmental analysis (NCA). Concentrations collected that are BQL before the first measurable PK concentration above the LLOQ will be treated as 0 for plotting and for all calculations including NCA and concentration summary statistics. The first BQL concentration after the last measurable PK concentration will be imputed as  $\frac{1}{2}$  LLOQ. Otherwise, BQL concentrations will be imputed as missing. Otherwise, PK sample concentrations that are BQL will be imputed as missing.

There will be no imputation for missing concentrations. The geometric mean (GM) of concentrations will be calculated using non-missing values after imputations.

Collection of plasma samples outside of the protocol defined time window for the time point, determined by exact rather than nominal time of collection, will not result in exclusion of the sample result from NCA. Plasma samples collected out of window will be evaluated on a case-by-case basis. Results from PK plasma samples that were collected substantially outside of the protocol-defined time window will be excluded from concentration summary statistics by nominal time points and plots of mean concentration by nominal time point. Substantially out-of-window samples will be defined as twice the size of the protocol-defined windows. Plasma will be drawn at the following time points to measure the concentration of SLV213 and analyze PK parameters:

- On Day 1 MORNING DOSE: Within 30 min before the morning dose ( $t=0$ ), and at 0.5h ( $\pm 5$  min), 1h ( $\pm 5$  min), 2h ( $\pm 5$  min), 4h ( $\pm 5$  min), 6h ( $\pm 10$  min), 8h ( $\pm 10$  min), and 12h ( $\pm 15$  min) after the morning dose. (The 12h time point is the same as the pre-dose time point ( $t=0$ ) before the evening dose on Day 1)
- On Day 1 EVENING DOSE: Before ( $t=0$ ) and 12h ( $\pm 15$  min) after the evening dose. (The 12h time point is the same as the pre-dose time point before the morning dose on Day 2).
- On Days 2 to 6: Within 30 min before the morning and evening doses ( $t=0$ ) and at 12h ( $\pm 15$  min) after the morning and evening doses on each day. (The PK time point before each dose on Days 2 to 6 is the same as the 12h time point of the previously received dose.)
- On Day 7 MORNING DOSE: Within 30 min before the morning dose ( $t=0$ ), and 12h ( $\pm 15$  min) after the morning dose. (The 12h time point is the same as the pre-dose time point ( $t=0$ ) before the evening dose on Day 7)
- On Day 7 EVENING DOSE: Within 30 min before the evening dose ( $t=0$ ), and at 0.5h ( $\pm 5$  min), 1h ( $\pm 5$  min), 2h ( $\pm 5$  min), and 4h ( $\pm 5$  min) after the evening dose on Day 7.
- On Day 8: At 6h ( $\pm 10$  min), 8h ( $\pm 10$  min), 12h ( $\pm 15$  min) and 24h ( $\pm 15$  min) after the evening dose on Day 7.
- On Day 9: At 36h ( $\pm 15$  min) and 48h (-2 hours) after the evening dose on Dose 7.

If the exact time of plasma PK sample collection is not recorded, then the collection time will be imputed as the planned time for analysis, as long as it is not known that the sample was collected outside of the protocol-defined window. Rationale for excluding results from analysis will be described in the CSR. Results from samples with imputed collection times will be indicated in listing of PK sample concentrations.

Participant-level SLV213 concentration listings will include separate columns for concentrations reported by the lab and concentrations used for analysis ([Listing 9](#)). The lab reported concentrations may include codes

such as “BQL” or “QNS” (Quantity Not Sufficient), while the analysis concentrations will contain numeric data only, including imputed values such as 0 for pre-dose time points and BQL samples prior to the first quantifiable sample. Listing will also indicate nominal time (i.e., planned time point) and actual time post dose in hours and minutes (e.g., 12H 10M). The listing will also indicate sample times that were collected out of window or imputed.

Individual concentrations for all participants in the PK population will be presented in tables and figures:

1. Summary statistics of SLV213 concentrations in plasma are presented for each nominal time point on Day 1 (morning dose) ([Table 15](#) and [by sex] [Table 16](#)), Day 1 (evening dose) to Day 7 (morning dose) ([Table 17](#) and [by sex] [Table 18](#)), and Day 7 (evening dose) to Day 9 ([Table 19](#) and [by sex] [Table 20](#)).
2. Individual SLV213 concentrations in plasma profiles are presented graphically for Day 1 (morning dose) ([Figure 3](#)) and Day 7 (evening dose) ([Figure 4](#)).
3. Individual trough SLV213 concentrations in plasma profiles are presented for Day 1 (morning dose) through Day 7 (evening dose) ([Figure 5](#)).
4. Semi-log individual SLV213 concentrations in plasma profiles are presented for Day 1 (morning dose) ([Figure 6](#)) and Day 7 (evening dose) ([Figure 7](#)).
5. Semi-log individual trough SLV213 concentrations in plasma profiles are presented for Day 1 (morning dose) to Day 7 (evening dose) ([Figure 8](#)).

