**LIST OF ABBREVIATIONS**

AE	Adverse Event
AESI	Adverse Event of Special Interest
ALT	Alanine Aminotransferase
ALP	Alkaline Phosphatase
aPTT	Activated Partial Thromboplastin Time
AST	Aspartate Aminotransferase
ATC	Anatomical Therapeutic Chemical
AUC	Area under the plasma concentration-time curve
AUC (0-t)	AUC from time zero to the last time with a concentration greater than or equal to the validated limit of quantitation of the assay
AUC (0-∞)	AUC from time zero to infinity
AUC (0-12)	AUC from 0h (time zero [pre-dose]) to 12h after dosing
AUC (0-48),ss	AUC from 0h (time zero [pre-dose]) to 48h after dosing at steady state
AUC (0-last)	AUC from time zero to the last concentration above the LLOQ
AUC (0-tau)	AUC from time zero to the end of the dosing interval
AUC (0-tau),ss	AUC from time zero to the end of the dosing interval at steady state
BID	Bis In Die (twice a day)
BMI	Body Mass Index
BP	Blood Pressure
bpm	Breaths Per Minute
BQL	Below Quantifiable Limit
BUN	Blood Urea Nitrogen
C	Celsius
C avg	Average concentration during the dosing interval
CHEM	Chemistry
CI	Confidence Interval
CKD-EPI	Chronic Kidney Disease Epidemiology Collaboration
CL T	Total clearance
C max	Observed maximum concentration

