#### **6.5.3. BQL Data**

PK sample concentrations below the quantitative limit (BQL) will be imputed as zero if they did not come after a PK sample concentration that is above the lower limit of quantitation (LLOQ). The first PK sample that's BQL will be imputed as  $\frac{1}{2}$  LLOQ if it came after a PK sample concentration above LLOQ and all PK samples after are also BQL. Otherwise, PK sample concentrations that are BQL will be imputed as missing.

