## AUC

$AUC_{0-\text{last}}$  is defined as the area under the concentration-time curve from dosing ( $t=0$ ) to the time of the last measured concentration.  $AUC_{0-\text{last}}$  will be estimated using the Linear Up Log Down calculation method and obtained from the  $AUC_{\text{last}}$  parameter calculated by WinNonlin®.

$AUC_{0-\infty}$  is defined as the total area under the concentration-time curve from dosing ( $t=0$ ) taken to the limit as the end time becomes arbitrarily large.  $AUC_{0-\infty}$  can be calculated by adding  $AUC_{0-\text{last}}$  to an extrapolated value equal to the last measured concentration greater than the LLOQ divided by  $Ke$ :

$$AUC_{0-\infty} = AUC_{0-\text{last}} + \frac{C_{\text{last}}}{Ke}$$

Where  $C_{\text{last}}$  is the last measured concentration  $\geq$  LLOQ.  $AUC_{0-\infty}$  will be obtained from the  $AUC_{\text{INF\_obs}}$  parameter calculated by WinNonlin®.

% $AUC_{\text{ex}}$  is defined as percentage of  $AUC_{0-\infty}$  obtained by extrapolation from time of the last measured concentration to infinity. % $AUC_{\text{ex}}$  can be calculated by dividing AUC from time of the last measured concentration to infinity by  $AUC_{0-\infty}$ :

$$\%AUC_{\text{ex}} = \frac{AUC_{0-\infty} - AUC_{0-\text{last}}}{AUC_{0-\text{inf}}},$$

If % $AUC_{\text{ex}}$  is  $>20\%$ , the estimated  $AUC_{0-\infty}$  will be excluded from statistical summaries of PK parameter estimates and downstream calculations. % $AUC_{\text{ex}}$  will be obtained from the  $AUC\%Extrap\_obs$  parameter calculated by WinNonlin®.

$AUC_{0-12}$  will be calculated as the AUC extrapolated to 12 h after dosing. This will be obtained from the WinNonlin®  $AUC0\_12$  parameter.

$AUC_{0-\text{tau}}$  will be calculated as the AUC to the end of the dosing interval. The dose-normalized parameter  $AUC_{0-\text{tau}}/\text{Dose}$  will also be reported. These parameters will be obtained from the  $AUC_{\text{tau}}$  and  $AUC_{\text{tau}}_D$  parameters in WinNonlin®, respectively.

All AUCs will be reported in units of ng\*h/mL.

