## 16.2.6 Pharmacokinetics

### Listing 9: 16.2.6.1: Participant-Level SLV213 Concentrations in Plasma

**[Implementation Note:** Units of nominal time and actual time may vary by time point and will be provided for each time rather than in the column header. “Laboratory Reported Concentrations” will give the verbatim value reported by the lab (with minimal formatting, as needed) and will use the character value such as PC.PCORRES. “Analysis Concentrations” will report the value actually used for analysis and will use a numeric variable such as ADNCA.AVAL. If one or more samples are excluded from NCA, two additional columns will be provided in the PK report listing: “Excluded from NCA (Yes/No)” and “Reason for Exclusion from NCA”.

In the actual time column, mark out-of-window times with one asterisk (\*), substantially out of window visits with two asterisks (\*\*), and imputed times with three asterisks (\*\*\*)�. If there are no out-of-window times or imputed values, remove their respective footnotes.

Listing will be sorted by Treatment Group, Participant ID, Study Day, and Nominal Time.]

Treatment Group	Participant ID	Study Day (Dose)	Nominal Time	Actual Time	Laboratory Reported Concentrations (ng/mL)	Analysis Concentrations (ng/mL)
		Day 1 (Morning)	0	0	0	0
		Day 1 (Morning)	30M	28M	BQL	0
		Day 1 (Morning)	1H	1H 12M*	207	207

\*Out-of-window collection time.

\*\*Substantially out-of-window collection time.

\*\*\*Imputed time.

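### The SAP sets the first trailing BQL concentration to half LLOQ without exempting the NCA, which conflicts with its own definitions of Clast, AUC(0-t) and AUC(0-last)

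*SAP*

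**What the plan says.** **Imputation.** SAP 6.5.3 and Section 10 give three rules. BQL values before the first quantifiable sample are zero. The first BQL after the last quantifiable sample is half LLOQ: "The first BQL concentration after the last measurable PK concentration will be imputed as" half the LLOQ. All other BQL values are missing. Section 6.5.3 adds a condition to the half-LLOQ rule: it applies "if it came after a PK sample concentration above LLOQ and all PK samples after are also BQL".

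**Use in analysis.** For leading BQLs, Section 10 says they "will be treated as 0 for plotting and for all calculations including NCA and concentration summary statistics". The trailing-BQL sentence has no such words, and no words that exempt the NCA. Section 10 then describes the participant-level listing, which shows laboratory-reported values in one column, "while the analysis concentrations will contain numeric data only, including imputed values such as 0 for pre-dose time points". The Listing 9 shell says the analysis column "will report the value actually used for analysis and will use a numeric variable such as ADNCA.AVAL".

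**Definitions.** SAP 10.1.1 builds AUC(0-inf) by adding to AUC(0-last) "an extrapolated value equal to the last measured concentration greater than the LLOQ divided by" Ke, and states that Clast is at or above the LLOQ. The List of Abbreviations defines AUC(0-last) as "AUC from time zero to the last concentration above the LLOQ". AUC(0-t) ends at the last concentration at or above the quantitation limit.

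**Slope.** SAP 10.1 and 10.1.1 take Ke points first from the WinNonlin algorithm. They require points after Tmax, at least three of them, and adjusted R-squared of at least 0.90. The analyst may choose points manually instead.

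**The concern.** A half-LLOQ value is neither measured nor at or above the LLOQ. If it is in the NCA input, the imputation rule and the Clast and AUC(0-last) definitions cannot both be followed. A programmer has to choose, and the text leans towards including the value.

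The consequences would spread. The SAP reads Cmin and Cmin,ss from WinNonlin's Clast, and Tmin from Tlast, so an imputed number would be reported as an observed minimum. AUClast would run one sampling time further. The last point used for extrapolation would change, and with it the percentage extrapolated, which decides whether AUC(0-inf), clearance and Vd are summarised. No Ke criterion keeps the value out of the slope, so half-life, clearance and volume are exposed too. These are secondary endpoints, and only the 400 mg cohort remains, so there are few profiles to absorb a distorted one.

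The late Day 7 samples (12, 24, 36 and 48 h) are 12 h apart. The true concentration at the imputed time can therefore lie well below half LLOQ, or above it, and the direction of the error varies.

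**Working it through.** The plan states no figure to reproduce, so the check has two parts.

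**1. Text.**
- Imputed value: half LLOQ (SAP 6.5.3 and 10).
- Value analysed: the imputed analysis concentration (Section 10, Listing 9).
- Clast for AUC(0-inf): at or above LLOQ (10.1.1).
- End of AUC(0-last): above LLOQ (Abbreviations, Section 3).
- Slope points: no LLOQ condition (10.1, 10.1.1).

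The first two and the next two are incompatible for any profile that ends in a BQL sample.

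**2. Illustration.** From the SAP: Day 7 evening-dose times 0, 0.5, 1, 2, 4, 6, 8, 12, 24, 36 and 48 h; linear-up log-down AUC; uniform weighting; at least three points after Tmax. Assumed: one-compartment oral profile without noise, ka 1.5/h, pre-dose value zero, LLOQ = 1 unit, automatic slope chosen by best adjusted R-squared among windows ending at the last retained value. Each profile was analysed with the trailing BQL left out and then with it set to 0.5.

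| True half-life | LLOQ, % of Cmax | True value at imputed time (LLOQ units) | Half-life, BQL out | Half-life, 0.5 in | Change | Adjusted R-squared, 0.5 in |
|---|---|---|---|---|---|---|
| 2 h | 2% | 0.025 | 2.01 | 3.38 | +68% | 0.89 |
| 2 h | 0.5% | 0.099 | 2.01 | 2.58 | +28% | 0.98 |
| 2 h | 0.1% | 0.493 | 2.01 | 2.01 | 0% | 1.00 |
| 3 h | 10% | 0.065 | 3.01 | 5.58 | +85% | 0.86 |
| 4 h | 10% | 0.234 | 4.01 | 5.19 | +29% | 0.98 |
| 6 h | 2% | 0.262 | 6.00 | 6.61 | +10% | 0.99 |
| 6 h | 10% | 0.839 | 6.02 | 4.61 | -23% | 0.99 |

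Fit quality matters here. The +85% and +68% fits fall below 0.90, so the automatic slope would not be accepted. Others pass: at half-life 2 h and LLOQ 1% of Cmax the fit gives 2.92 h with adjusted R-squared 0.950, and 2.92/2.01 = 1.45, an accepted error of +45%. At half-life 2 h and LLOQ 3% it gives 3.71 h with 0.836, which fails. Without the imputed point, that profile keeps four points after Tmax and returns 2.01 h with R-squared 1.000.

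**Extrapolation, half-life 6 h and LLOQ 10% of Cmax.** AUC(0-inf) = AUC(0-last) + Clast/Ke, with Ke = ln 2/half-life.
- BQL out: Ke = 0.693/6.02 = 0.115; 3.35/0.115 = 29.1; AUC(0-inf) = 77.3 + 29.1 = 106.5; extrapolated 29.1/106.5 = 27%.
- Half LLOQ in: the 12 to 24 h segment adds 12 × (3.35 - 0.5)/ln(3.35/0.5) = 18.0, so AUClast = 95.3 (+23%); Ke = 0.693/4.61 = 0.150; 0.5/0.150 = 3.3; AUC(0-inf) = 98.7; extrapolated 3.3/98.7 = 3%.

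A value that the 20% rule would exclude is kept. With 14 doses of accumulation instead of a zero pre-dose value, the same case goes from 26.7% to 3.4%.

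**Day 1.** Half-lives of 1.5, 2, 3, 4 and 6 h were crossed with the four LLOQ levels in the table. Only three of these 20 profiles reach BQL by 12 h. In those three, AUC(0-last) rises by 3% (170.89 to 176.51), 6% (32.19 to 34.03) and 8% (40.16 to 43.46), if the rule applies there at all.

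**The case against.** The strongest reply is that the SAP never says the trailing half-LLOQ value enters the NCA. The phrase about all calculations including NCA belongs to the leading-BQL sentence. The half-LLOQ footnote appears under concentration Tables 15, 17 and 19, and not under the parameter Table 21. Section 10's examples of imputed values are pre-dose and leading BQLs. Listing 9 also allows columns for samples excluded from NCA. On this reading, half LLOQ serves the concentration summaries, the specific Clast definition governs the NCA, and nothing conflicts.

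Part of this stands: entry into the NCA is inferred. The inference is strong, because no passage exempts the NCA and Listing 9 points to the imputed variable as the one analysed. If the exempting reading is intended, the SAP should say so, and the same sentence does it.

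Three further points also stand.
- The documents do not describe how the software treats the value. That it becomes Clast is the normal result; that it becomes a slope point is permitted, not assured.
- A reader might infer that a poor automatic fit removes a participant from Table 21. SAP 10.1.1 lets the analyst choose other points, so that loss is possible, not certain. Manual selection repairs the slope only; it does not restore Clast, Tlast or AUClast.
- AUC(0-last) and AUC(0-inf) are Day 1 endpoints, where sampling gaps are at most 4 h. If the 6.5.3 condition is judged over a participant's whole series, a Day 1 BQL followed by later quantifiable samples is missing, and the rule does not act on Day 1.

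The analyses are descriptive, and Listing 9 would show any imputed value beside the laboratory result.

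**Conclusion.** The point holds as an unresolved conflict in the SAP. The imputation rule has no NCA exception, the listing shell points to imputed values being analysed, and Clast, AUC(0-t) and AUC(0-last) are defined by concentrations at or above the LLOQ. If the value enters the NCA, Clast, Tlast, AUClast and the extrapolated percentage would normally be wrong by the SAP's own definitions, and the slope may be biased in either direction.

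The exposure lies mainly on Day 7: half-life, clearance, volume, Cmin,ss and Tmin. Day 1 is reached, for a participant with later quantifiable samples, only if the 6.5.3 condition is judged per profile.

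The size for SLV213 is unknown. The range of -23% to +85% for half-life belongs to the assumed grid (one compartment, no noise, half-life 2 to 6 h, LLOQ 0.1% to 10% of Cmax) and describes automatic fits before the Ke criterion is applied. It should not be read as a prediction of bias, nor as evidence that participants will be lost from Table 21.

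**What to change.** In SAP 6.5.3 and 10:
- set all BQL values after the last quantifiable concentration in a profile to missing for NCA;
- confine the half-LLOQ rule to concentration summaries and plots;
- state that both rules are applied per dosing profile.

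In SAP 10.1, add to the Ke criteria that every slope point must be at or above the LLOQ.

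The cost is a sentence or two in the SAP and one line in the NCA dataset specification, with no change to trial conduct. Some profiles may then exceed the 20% extrapolation limit and drop out of the AUC(0-inf) and clearance summaries, which is what that limit is for. SAP Section 15 rules out amendment after final data lock, so the change belongs in an amendment or addendum before then. After lock, the clinical study report should state which rule was used in the NCA.

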## 10.1. Noncompartmental Analysis

PK parameters from plasma PK data will be estimated through NCA using version 8.3.4 or higher of Phoenix WinNonlin®. Actual post dose times will be used for estimation of plasma PK parameters instead of nominal time. In case of imputed sample collection times, the imputed time will be included in NCA. Any outliers identified in the PK analysis will be discussed in the analysis report. Outliers will not be excluded from the noncompartmental PK analysis.

All estimable participant-specific PK parameters for single-dose and multiple dose are included in [Listing 10](#) and [Listing 11](#), respectively.

Summary statistics for SLV213 PK parameters are presented by Day 1, Single Dose and Day 7, Multiple Dose for the 400 mg SLV213 treatment group ([Table 21](#)) for participants in the PK population with a measurable Ke (terminal elimination rate constant) at the given dose.

The definition of coefficient of variation (CV%) is described below:

For an independent identically distributed random sample  $\{x_1, x_2, \dots, x_n\}$  from a log-normal distribution, let  $s^2$  be the sample variance statistic of the natural log-transformed values of the sample. The CV% will be defined as:

$$CV\% = \sqrt{\exp(s^2) - 1} \times 100\%$$

Phoenix WinNonlin® NCA will use the following settings to compute parameters from plasma PK data:

- Linear Up Log Down calculation method
- Uniform weighting
- Ke Acceptance Criteria
  - Rsq\_adjusted  $\geq 0.90$

---

- Includes at least 3 time points after  $T_{max}$

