#### **Cmax**

$C_{max}$  is defined as the maximum drug or metabolite concentration observed in plasma over all PK sample concentrations. It will be obtained from the  $C_{max}$  parameter calculated by WinNonlin®. If there is no measurable concentration in the participant's PK profile, then  $C_{max}$  will be missing for that participant.  $C_{max}$  will be reported in units of ng/mL. The dose-normalized parameter  $C_{max}/Dose$  will also be reported from  $C_{max\_D}$  in WinNonlin®.

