#### **Cmin**

$C_{min}$  is defined as the observed minimum concentration at the end of the dosing interval. It will be obtained from the  $C_{last}$  parameter calculated by WinNonlin®.

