#### **Tmax**

Time of maximum concentration ( $T_{max}$ ) is defined as the time at which the  $C_{max}$  occurs. It will be obtained from the  $T_{max}$  parameter calculated by WinNonlin®. If there is no measurable  $C_{max}$  in the participant's PK profile, then  $T_{max}$  will be missing for that participant.  $T_{max}$  will be reported in units of h.

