**Table 21: Summary Statistics for SLV213 PK Parameters by Dose, 400 mg SLV213 PK Population**

[Implementation Note: PK parameters will only be summarized for participants with a measurable Ke at the specified dosing day.]

PK Parameter (Units)	N	Mean (SD)	GM (CV%)	Median	Minimum, Maximum
Day 1, Single Dose					
C max (ng/mL)	x	xx.x (xx.x)	xx.x (xx.x)	xx.x	xx, xx
C max /Dose (ng/mL/mg)	x	xx.x (xx.x)	xx.x (xx.x)	xx.x	xx, xx
C min (ng/mL)	x	xx.x (xx.x)	xx.x (xx.x)	xx.x	xx, xx
T max (h)	x	xx.x (xx.x)	xx.x (xx.x)	xx.x	xx, xx
AUC (0-t) (ng*h/mL)	x	xx.x (xx.x)	xx.x (xx.x)	xx.x	xx, xx
AUC (0-∞) (ng*h/mL)	x	xx.x (xx.x)	xx.x (xx.x)	xx.x	xx, xx
AUC (0-12) (ng*h/mL)	x	xx.x (xx.x)	xx.x (xx.x)	xx.x	xx, xx
AUC (0-last) (ng*h/mL)	x	xx.x (xx.x)	xx.x (xx.x)	xx.x	xx, xx
AUC (0-tau) (ng*h/mL)	x	xx.x (xx.x)	xx.x (xx.x)	xx.x	xx, xx
AUC (0-tau)/Dose (ng*h/mL/mg)	x	xx.x (xx.x)	xx.x (xx.x)	xx.x	xx, xx
t 1/2 (h)	x	xx.x (xx.x)	xx.x (xx.x)	xx.x	xx, xx
CL T (L/h)	x	xx.x (xx.x)	xx.x (xx.x)	xx.x	xx, xx
Ke (1/h)	x	xx.x (xx.x)	xx.x (xx.x)	xx.x	xx, xx
Vd (L)	x	xx.x (xx.x)	xx.x (xx.x)	xx.x	xx, xx
Day 7, Multiple Doses					
C max,ss (ng/mL)	x	xx.x (xx.x)	xx.x (xx.x)	xx.x	xx, xx
C max /Dose (ng/mL/mg)	x	xx.x (xx.x)	xx.x (xx.x)	xx.x	xx, xx
C min,ss (ng/mL)	x	xx.x (xx.x)	xx.x (xx.x)	xx.x	xx, xx
C avg (ng/mL)	x	xx.x (xx.x)	xx.x (xx.x)	xx.x	xx, xx
RC max a	x	xx.x (xx.x)	xx.x (xx.x)	xx.x	xx, xx
T max,ss (h)	x	xx.x (xx.x)	xx.x (xx.x)	xx.x	xx, xx
T min (h)	x	xx.x (xx.x)	xx.x (xx.x)	xx.x	xx, xx
AUC (0-48),ss (ng*h/mL)	x	xx.x (xx.x)	xx.x (xx.x)	xx.x	xx, xx
AUC (0-tau),ss (ng*h/mL)	x	xx.x (xx.x)	xx.x (xx.x)	xx.x	xx, xx
AUC (0-tau)/Dose (ng*h/mL/mg)	x	xx.x (xx.x)	xx.x (xx.x)	xx.x	xx, xx
Linearity Index b	x	xx.x (xx.x)	xx.x (xx.x)	xx.x	xx, xx

PK Parameter (Units)	N	Mean (SD)	GM (CV%)	Median	Minimum, Maximum
RAUC c	x	xx.x (xx.x)	xx.x (xx.x)	xx.x	xx, xx
t 1/2 (h)	x	xx.x (xx.x)	xx.x (xx.x)	xx.x	xx, xx
CL T (L/h)	x	xx.x (xx.x)	xx.x (xx.x)	xx.x	xx, xx
Vd,ss (L)	x	xx.x (xx.x)	xx.x (xx.x)	xx.x	xx, xx

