Note: Single-dose parameters are calculated over the 12-hour period following the morning dose (Dose 1) on Day 1. Multiple-dose parameters are calculated over the 48-hour period following the evening dose (Dose 14) on Day 7.

N = Number of participants with an estimable Ke for the given dose used to calculate summary statistics.

SD = Standard Deviation; GM = Geometric Mean; CV = Coefficient of Variance.

a RCmax is defined as the accumulation ratio for Cmax estimated as Cmax (Day 7, Evening Dose)/Cmax (Day 1, Morning Dose).

b Linearity index is estimated as AUC(0-tau),ss (Day 7, Evening Dose)/AUC(0-x) (Day 1, Morning Dose)

c RAUC is defined as the accumulation ratio for AUC estimated as AUC(0-tau) (Day 7)/AUC(0-tau) (Day 1).

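### Table 21 applies the Ke acceptance filter to every PK row, so Day 1 Cmax, Tmax, Cmin and AUC(0-last), which need no Ke, lose participants with a late peak or a poor terminal fit

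*SAP*

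**What the plan says.** Three places in the SAP state the restriction, and they agree:

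- SAP 10.1 says Table 21 is produced "for participants in the PK population with a measurable Ke (terminal elimination rate constant) at the given dose".
- The implementation note to Table 21 says "PK parameters will only be summarized for participants with a measurable Ke at the specified dosing day".
- The Table 21 footnote says "N = Number of participants with an estimable Ke for the given dose used to calculate summary statistics".

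The Ke acceptance criteria in SAP 10.1 are an adjusted R-squared of at least 0.90 and a fit that "Includes at least 3 time points after" Tmax.

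SAP 10.1.1 defines several of the tabulated parameters without Ke:

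- Cmax "is defined as the maximum drug or metabolite concentration observed in plasma over all PK sample concentrations".
- Tmax "is defined as the time at which the" maximum occurs.
- Cmin "is defined as the observed minimum concentration at the end of the dosing interval. It will be obtained from the" Clast output.
- AUC(0-last) runs from dosing "to the time of the last measured concentration".

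The Ke paragraph of SAP 10.1.1 separately lists what becomes missing when Ke is not accepted: Ke itself, t1/2, AUC(0-∞), CLT and Vd.

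SAP 6.1 assigns PK summaries to the PK population. Neither SAP 6.3.4 nor protocol 9.3.3 puts a Ke condition on that population. Listings 10 and 11 show all estimable parameters whatever the Ke result, and Tables 15 to 20 (concentrations) are not filtered on Ke.

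**The concern.** The parameters that depend on Ke are already set to missing when Ke fails. The extra filter on the whole table therefore mainly removes valid values from rows that never needed Ke. Whether a participant is removed depends on that participant's own profile: a late peak, or a slow or irregular decline, leads to exclusion. That is selection on the outcome being summarised.

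Table 21 is the only table that summarises the secondary-endpoint PK parameters. The active group is small: 8 planned, and 8 to 12 once the four replacement participants in SAP 6.2 are allowed for (SAP Table 4 shows 6). Losing one or two people changes a row noticeably.

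Two further points follow:

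- The Linearity Index sits in the Day 7 block and is filtered on Day 7 Ke. The Ke it needs is Day 1's, through AUC(0-∞).
- Table 11 has no Ke-based exclusion reason, and Listing 5 must match Table 11. Neither would explain a reduced N in Table 21.

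**Working it through.** The plan gives no figure to reproduce here. The check is a count from the documents, followed by an illustration on stated assumptions.

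**Step 1: samples after Tmax.** The inputs are the nominal times in the notes to SAP Tables 15 and 19 and the three-point rule in SAP 10.1. Day 1 post-dose times are 0.5, 1, 2, 4, 6, 8 and 12 h. Day 7 adds 24, 36 and 48 h.

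| Tmax (h) | Later samples, Day 1 | Later samples, Day 7 |
|---|---|---|
| 0.5 | 6 | 9 |
| 1 | 5 | 8 |
| 2 | 4 | 7 |
| 4 | 3 (just passes) | 6 |
| 6 | 2 (fails) | 5 |
| 8 | 1 (fails) | 4 |
| 12 | 0 (fails) | 3 (just passes) |
| 24, 36, 48 | not sampled | 2, 1, 0 (fail) |

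So 3 of the 7 Day 1 post-dose times can never appear as Tmax in Table 21. On Day 7 it is 3 of 10, all at 24 h or later. This step needs no assumption about the drug.

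**Step 2: are the values computable without Ke?** Two invented Day 1 profiles were run through a linear-up log-down calculation.

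- Tmax 6 h: Cmax 300, Cmin 110 and AUC(0-last) 1948 are all available, but Ke is missing because only 2 points follow the peak.
- Tmax 2 h with an irregular tail: Cmax 300, Cmin 70 and AUC(0-last) 1452 are all available, but the best adjusted R-squared is 0.27, so Ke is rejected.

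Both participants would disappear from every Day 1 row.

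**Step 3: chance of losing someone.** For n participants and an assumed Ke-failure rate p, the chance of losing at least one is 1 − (1 − p)^n. With n = 8 and p = 0.10 this is 1 − 0.9^8 = 0.57. For p = 0.05, 0.20 and 0.30 it is 0.34, 0.83 and 0.94. With n = 6 and p = 0.10 it is 0.47.

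**Step 4: illustrative size.** The documents give no half-life, Tmax or variability, so all of these inputs are assumed:

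- one-compartment oral model, ka 0.3 to 2.0 per hour, half-life 2 to 8 h, residual error 5 to 20%;
- between-subject log-SD 0.4 for ka and 0.3 for ke and V;
- 20,000 Day 1 profiles per setting;
- Ke from the best adjusted R-squared over the last three or more points after Tmax with a negative slope.

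| ka (/h), half-life, error | Retained % | Out: late Tmax % | Out: poor fit % | Mean Tmax, all vs retained (h) | Cmin ratio |
|---|---|---|---|---|---|
| 2.0, 2 h, 10% | 99.9 | 0.0 | 0.1 | 1.12 vs 1.12 | 1.00 |
| 1.0, 4 h, 15% | 78.9 | 2.9 | 18.3 | 2.34 vs 2.11 | 0.89 |
| 1.0, 8 h, 15% | 40.9 | 15.3 | 43.8 | 3.27 vs 2.54 | 0.85 |
| 0.6, 6 h, 15% | 42.0 | 24.6 | 33.5 | 3.94 vs 2.95 | 0.82 |
| 0.3, 4 h, 15% | 33.5 | 41.1 | 25.4 | 4.83 vs 3.39 | 0.77 |
| 0.5, 8 h, 20% | 17.6 | 45.4 | 37.0 | 5.00 vs 3.22 | 0.80 |
| 0.3, 8 h, 20% | 8.0 | 67.8 | 24.3 | 6.30 vs 3.60 | 0.77 |

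The Cmin ratio is the geometric mean in retained participants divided by that in all participants. Over the settings examined, the same ratio is 0.99 to 1.08 for Cmax and 0.96 to 1.05 for AUC(0-12). At 5% error, retention is 98.9% for (1.0, 4 h), 60.3% for (0.3, 4 h) and 21.7% for (0.3, 8 h). Day 7 retention (4,000 profiles per setting, 14 doses) is 98 to 100%, but no quantitation limit was modelled.

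**The case against.** The wording and the count are not in dispute. The case against is that the consequence is small.

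- **The values survive elsewhere.** When the 12 h sample is quantifiable, Day 1 Cmin is the 12 h concentration, which Table 15 summarises for the whole PK population. Each Tmax is in Listing 10. The footnote discloses the rule. All this is true, and it limits the harm, but the Table 21 rows remain unrepresentative of the PK population.
- **The illustration overstates fit failure.** SAP 10.1.1 lets the PK analyst choose points manually. If any qualifying subset of points after Tmax is allowed, which is the most that manual choice could rescue, a separate run of 3,000 profiles cut fit failure from 43.5% to 27.0% at (1.0, 8 h, 15%) and from 18.6% to 8.5% at (1.0, 4 h, 15%). At (0.3, 4 h, 15%) it fell only from 23.4% to 20.5%. This stands, so the fit-failure column is an upper range. Late-Tmax exclusions do not change.
- **The extreme settings look unlikely.** Protocol 2.3.1 says predicted levels at 400 mg twice daily are well below the 800 mg single-dose Cmax. Assuming dose proportionality, (0.3, 8 h) puts the steady-state Cmax at 91% of that value, (0.3, 4 h) at 66% and (1.0, 4 h) at 59%. This makes the last table row less plausible but does not rule out slow absorption.
- **A specific rule may narrow a general one.** SAP 10.1 can be read as a deliberate subset of the PK population, so SAP 6.1 and 6.3.4 are not strictly contradicted. That is fair; the defect is what the subset does to rows that do not use Ke.
- **The trial stopped after Cohort 1 and tests no hypothesis.** This lowers the stakes, but the 400 mg PK summary is still planned.

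**Conclusion.** The concern holds. Applied as written, the SAP caps the Day 1 Tmax row at a nominal 4 h. It also removes valid Day 1 Cmax, Cmax/Dose, Cmin, AUC(0-t) and AUC(0-last) values for reasons tied to the shape of the profile. The cap follows from the sampling times and the three-point rule alone.

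The realised size depends on kinetics that the documents do not give. On the assumed model it is nil to large for Day 1 N and Tmax, nil to moderate for Day 1 Cmin, and small for Cmax and AUC(0-12). Day 7 is affected by point count only if Tmax is 24 h or later, and otherwise only by poor fit. AUC(0-12) and AUC(0-tau) are not wholly free of Ke, because they may need extrapolation when the 12 h sample is early or missing. This should be fixed, though it does not threaten the trial's safety conclusions.

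**What to change.** In SAP 10.1, the Table 21 note and the Table 21 footnote, apply the Ke condition only to rows that use Ke, and on the day whose Ke they use:

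- Day 1: Ke, t1/2, AUC(0-∞), CLT and Vd.
- Day 7: t1/2, CLT and Vd,ss.
- Linearity Index: through Day 1 AUC(0-∞), not Day 7 Ke.

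Summarise all other rows in the PK population wherever the value is estimable, with a row-specific n. For AUC(0-12), AUC(0-tau), AUC(0-48),ss and the quantities built on them (dose-normalised AUC, Cavg, RAUC), set only the individual value to missing when it needs extrapolation and Ke was not accepted. This follows the SAP's own practice for extrapolated area above 20%, which removes only AUC(0-∞), CLT and Vd.

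The cost is one sentence, one note, one footnote and row-specific n in the programming, with no new data. SAP 15 allows an addendum before final data lock but no amendment after it, so the change should be made before then.
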